1.0 Study Summary

Study Title	Safety Behavior Fading Intervention for Social Anxiety
Study Design	Randomized Control Trial
Primary Objective	To investigate the efficacy of a text message based safety behavior fading paradigm.
Secondary Objective(s)	Explore the effect of safety behavior fading on: 1) Levels of emotional disclosure. 2) Reductions in levels of perceived loneliness.
Research Intervention(s)/ Investigational Agent(s)	1) A control condition where participants are asked to participate in healthy behaviors 2) A safety behavior fading condition in which participants receive reminders to change their behavior.
Study Population	Adults aged 18-65
Sample Size	500
Study Duration for individual participants	Approximately 4 hours across a 4 week period.
Study Specific Abbreviations/ Definitions	

2.0 Objectives*

- 2.1 *The current study aims to explore the efficacy of a text message based Safety Behavior Fading Intervention compared to a control intervention.*
- 2.2 *We hypothesize that individuals practicing safety behavior fading will exhibit (1) decreased social anxiety symptoms and report (2) increased levels of emotional disclosure, and (3) greater reductions of perceived loneliness compared to the control group.*

3.0 Background*

- 3.1 *Safety behaviors are defined as behavioral strategies deemed necessary for preventing or minimizing a feared outcome. Theoretical models suggest that excessive use of safety behaviors may serve a casual and/or maintaining role among a range of psychopathology, including social anxiety disorder (Well et al., 1995), a disorder characterized by an intense fear of being judged or negatively evaluated by others, or rejected in a social or performance situation.. While social anxiety disorder causes both distressing and impairing symptoms, studies have begun to show a link between increased social anxiety and decreased self-disclosure, and resulting decreased feelings of emotional intimacy.*

4.0 Study Endpoints*

4.1 N/A

5.0 Study Intervention/Investigational Agent

5.1 Description: Social anxiety safety behavior fading intervention procedures will follow methodology previously used in the [name] Lab. The safety behavior fading intervention is designed to target a decrease or elimination of five social anxiety safety behaviors that an individual has self-identified that they engage in most frequently and/or to the greatest extent.

Individuals randomly assigned to the safety behavior fading condition will receive instructions to decrease or eliminate their five social anxiety safety behaviors. In addition, they will receive daily reminders via text message to decrease these behaviors, along with a safety behavior monitoring checklist in which the participant indicates the extent to which they decreased and/or eliminated each safety behavior over the previous day. The daily reminder will include the following language: “Hi! This is a friendly reminder to avoid using your checklist behaviors. Please tap the link below to access today’s checklist: [link to checklist].”

Individuals randomly assigned to the control condition will receive text messages to encourage fading of “unhealthy behaviors”. They will follow the same procedure as the safety behavior fading group.

6.0 Procedures Involved*

6.1 Participants will be recruited through online postings.

Once they sign up, all participants will be asked to provide informed consent before participating in the current study. After consenting, the participant will complete the first battery of self-report measures. If the participant scores a 30 or lower on the SPIN, they will not be eligible to participate

If they score a 30 or above on the SPIN and meet all eligibility criteria, participants will be randomly assigned to one of two experimental conditions: Safety Behavior (SB) Fading Condition or control condition. During this pre-assessment virtual appointment, participants will complete a questionnaire battery assessing related symptoms and concerns, as well as safety behaviors. Participants in the SB fade condition will select five behaviors from their completed Safety Avoidance Frequency Examination (SAFE) that they engage in the most. They will be informed that the researchers are interested

in the extent to which people can engage in these behaviors less than they normally do on a daily basis, for two weeks. Participants in the “healthy behaviors” group will be told they will be sent a checklist of healthy behaviors.

Participants will also receive instructions regarding how to complete their daily safety behavior monitoring checklist. They will receive 14 checklists via text over the course of the next two weeks (assessment period). Daily checklists will take roughly 5-minutes each.

At the end of four weeks all participants will be sent a second set of questionnaires via email to complete.

6.2 Screening: Social Phobia Inventory (SPIN; Connor et al., 2000)

Pre-assessment virtual appointment components:

Component 1: Self-Report Assessments – Participants will complete a battery of self-report measures that assess relevant constructs. The questionnaires included are:

- 1. Basic demographic information*
- 2. SCID-II Personality Questionnaire: Avoidant Personality Disorder (AVPD) Items (American Psychiatric Association, 1986)*
- 3. Center for Epidemiologic Studies Depression Scale (CESD; Radloff, 1977)*
- 4. Self-Disclosure Index (SDI; Miller et al., 1983)*
- 5. Emotional Self-Disclosure Scale (ESDS; Snell et al., 1988)*
- 6. UCLA Loneliness Scale (ULS; Hays & Dimatteo, 1987)*
- 7. Subtle Avoidance Frequency Examination (SAFE; Cuming et al., 2009)*
- 8. Social Phobia Inventory (SPIN; Connor et al., 2000)*

Component 2: Treatment rationale. Participants will receive the following treatment rationale:

Safety Behavior: Safety behaviors are behaviors we use to make us feel less anxious and prevent bad things from happening. For example, when in a social situation, some people might hide their faces so others won’t see them blush, or they may seek reassurance from others about things they said or how they look. Safety behaviors can be problematic because when we use them, we are never able to see that the outcome we fear doesn’t come true. We say to ourselves, “the reason nothing bad happened is because I got reassurance from others, I spoke softly, I didn’t draw attention to myself...” or used other safety behaviors. Safety behaviors can become a crutch and make you feel less confident in social situations. Research has found that dropping safety behaviors can help reduce anxiety.

Unhealthy Behaviors: Social anxiety like many other problems can keep us from taking care of ourselves. Engaging in unhealthy behaviors can make us feel even worse, and more anxious. For example, if people don't sleep or eat enough, they might tend to be tired and feel like they are less able to handle their anxiety. This can create a cycle where we engage in unhealthy behaviors because of our anxiety and then that can make our anxiety worse and then engage in more unhealthy behaviors as a result. Also, spending too much time on social media or not moving around enough might lower your confidence and make it harder for you in social situations. Research has found that decreasing certain unhealthy behaviors can make you more confident and help improve mood and anxiety.

They will then complete the Credibility/Expectancy Questionnaire (CEQ; Devilly & Borkovec, 2000).

twp-week assessment period:

Component 3: Safety Behavior Checklist (completed daily)

Post-treatment:

Component 4: Self-Report Assessments – Participants will complete a battery of self-report measures that assess relevant constructs. This battery will include all items from Component 1.

Component 7: Debriefing – All participants will be informed of the actual, full study purpose.

One month follow-up:

Component 8: Self-Report Assessments – Participants will complete a battery of self-report measures that assess relevant constructs. This battery will include all items from Component 1

6.3 *The potential risks associated with participation in this study appear to be minimal (see below). Nevertheless, precautions will be taken to minimize participants' risk in the proposed study. All individuals will be informed of the nature of the investigation and the types of assessments and procedures. Participants will be asked to sign an informed consent statement prior to participating in the project. Several safeguards for maintaining participant confidentiality will also be in place (see below). In addition, referrals to appropriate clinical services (e.g. FSU Psychology Clinic) will be provided for any participants seeking treatment.*

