13.0 Recruitment Methods

13.1 Participants will be recruited from across the United States through posting on internet websites such as Craigslist, Facebook, Reddit etc. Participants will be asked to sign consent before completing the SPIN and other screening questions.

13.2 Participants will be recruited from across the United States.

13.3 Participants who score at or above a 30 on the SPIN be invited to participate in the current study and provided with their questionnaire battery.

13.4 Potentially eligible participants will be contacted via email, with the initial questionnaire battery.

13.5 Participants will be entered into a raffle for 10 \$20 Amazon gift cards when they complete the post treatment assessment and will receive an additional entry into the raffle if they complete the one month follow up assessments. Raffles will occur at the end of 12 months of study enrollment. We anticipate participants will have 1 in 10 chance or greater of receiving a gift card. Participants email addresses will be retained until that time to deliver the gift cards. No other identifying information will be retained for this purpose.

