15.0 Risks to Subjects*

15.1 Risks to human subjects in the present study are believed to be minimal. Nevertheless, precautions will be taken to minimize participants' risk in the proposed study. All individuals will be informed of the general nature of the investigation and the types of assessments and procedures. Participants will be given an opportunity to have any questions answered to their satisfaction and then will be asked to sign an informed consent statement prior to participating in the project. The specific potential risks involved in the proposed investigation are enumerated below.

There are two main areas of risk:

1) Self-report Measures: Some participants may be hesitant to record their social anxiety and/or depressive symptoms on assessment forms. It is possible that questionnaires relating to social anxiety, depression, and perceived loneliness could lead to emotional discomfort for some participants.

2) Confidentiality: We will be collecting information about the participant that could cause social and psychological risk if released inappropriately.

The above areas of risk will be minimized by the following procedures:

1) Participants will be made aware that they are free to omit questions they feel uncomfortable answering and are free to terminate their participation at any time during the study without penalty. While some participants may be hesitant to answer the assessment forms, others may derive benefit from the self-assessment as it could increase their awareness of the relationship between their symptoms and environmental, cognitive, and interpersonal factors. Participants will be encouraged to contact study staff at any point during the study if they have questions or concerns. Referrals to appropriate clinical services (e.g., FSU Psychology Clinic, the Anxiety and Behavioral Health Clinic) will be provided for any participants seeking treatment. All research staff will be trained to deal with sensitive clinical issues and will be available during the assessment process should participants need assistance.

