17.0 Data Management* and Confidentiality

17.1 *2 X 2 mixed model ANOVAs will be conducted to evaluate the effect of the manipulation on study variables of interest.*

17.2 *Subjects' names and email addresses will be recorded upon their consenting to participate and used to send participants reminders about appointments. Further, participants in the SB Fade group will receive daily emails/texts during the two assessment weeks to remind them to complete their Behavior Checklist each day. However, no names or direct identifiers will be linked with the data collected over the course of the study. Each participant will be assigned a unique, codified Identification Code that is unrelated to the participants' identifying information. All questionnaires will be labeled using their codified Identification Code. The Key-file associating Identification Codes with participant names, email addresses, and phone numbers will be kept by the principal investigator separate from all other study data and consent forms in a secured file. Email addresses are needed in order to send links to and reminders for the online appointments. Phone numbers are needed in order to send daily text message reminders to participants in the SB Fade condition. If an individual is unable or unwilling to supply their phone number, daily reminders will be sent to their email address. All study data will be stored in de-identified databases in password protected files on encrypted computers.*

No individual will ever be publicly identified. We will only report results that have been averaged over participants. No records or assessment information will be released to any other person. All identifying information will be deleted after data collection is complete.

Participants will be informed that there are certain situations in which we may break confidentiality. If during the study we learn about child neglect, child or elder abuse, or that someone is a clear, serious, and direct harm to self or others, we may report the information to appropriate authorities, including the police or an emergency medical facility. Such a possibility is therefore explicitly stated in the consent document. All data and paperwork will be protected to the extent provided by law.

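### Participants are debriefed on the full study purpose before the one-month battery, so the one-month between-group comparison may be biased in an unknown direction; the post-treatment comparison is not affected

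*Protocol*

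**What the plan says.** Section 6.2 of the Protocol lists the later procedures in this order.

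- **Post-treatment:** Component 4 is the self-report battery. Component 7 is the debriefing: "All participants will be informed of the actual, full study purpose".
- **One month follow-up:** "Component 8: Self-Report Assessments", of which the protocol says "This battery will include all items from Component 1".

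Section 9.1 also puts the one-month follow-up after the post-treatment questionnaires. Section 13.5 rewards its completion: participants "will receive an additional entry into the raffle if they complete the one month follow up assessments". It is therefore a planned data point.

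On what participants know before the debriefing, section 6.3 says "All individuals will be informed of the nature of the investigation and the types of assessments and procedures", while section 15.1 says they will be "informed of the general nature of the investigation".

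The only stated analysis is in section 17.1, where 2 x 2 mixed "ANOVAs will be conducted to evaluate the effect of the manipulation on study variables of interest". The two time points are not named.

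**The concern.** The words actual and full in the debriefing text imply that participants had only a partial account until then. The design also tries to make the control task believable: section 6.2 contains a rationale for reducing unhealthy behaviors, and credibility and expectancy are measured straight after the rationale. Debriefing both arms before the last outcome measurement can undo this in two ways.

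1. **Control uptake.** Controls who learn that fading safety behaviors was the intervention under test can try it themselves. It needs no equipment or therapist. This would shrink the one-month difference.
2. **Reporting.** The outcome measures listed in section 6.2 are self-report. Once participants know which condition was expected to do better, either arm may answer differently, and the difference could shrink or grow.

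The one-month battery is the last measurement and the only evidence on whether any effect lasts. Because everyone is debriefed, no undebriefed group remains from which to estimate the bias. No later analysis can undo a disclosure already made.

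**Working it through.** **Order of events.** The protocol states no figure to reproduce here; the point rests on sequence.

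| Step | Section 6.2 | Relative to debriefing |
|---|---|---|
| Post-treatment battery | Component 4 | before, as listed |
| Debriefing of all participants | Component 7 | – |
| One-month battery | Component 8 | after |

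Nothing elsewhere in the protocol delays the debriefing or qualifies the later battery. That the post-treatment battery is safe rests on the listed order within the Post-treatment heading; there is no explicit timing rule, but nothing contradicts that order.

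**Illustration of size.** The protocol gives a total of 500 participants and no effect size, SD, allocation ratio, correlation or dropout. All of the following is assumed:

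- equal allocation, so 250 per arm, or 175 per arm at 70% retention (0.70 × 250 = 175);
- a true one-month difference of d = 0.30 SD without debriefing;
- a correlation of 0.5 between baseline and follow-up, so the change-score variance is 2(1 − 0.5) = 1 and SE = √(2/n);
- a share c of controls adopting fading, each gaining a share b of the full effect.

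SE = √(2/250) = 0.0894, or √(2/175) = 0.1069. The difference that remains is d(1 − cb). Power is two-sided at 5%, by normal approximation, with z = difference/SE.

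*Shrinkage from control uptake:*

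| n per arm | c | b | difference | power |
|---|---|---|---|---|
| 250 | 0 | – | 0.300 | 91.8% |
| 250 | 20% | 0.25 | 0.285 | 89.0% |
| 250 | 20% | 0.5 | 0.270 | 85.5% |
| 250 | 20% | 1 | 0.240 | 76.5% |
| 250 | 30% | 0.25 | 0.2775 | 87.3% |
| 250 | 30% | 0.5 | 0.255 | 81.4% |
| 250 | 30% | 1 | 0.210 | 65.1% |
| 175 | 0 | – | 0.300 | 80.1% |
| 175 | 20% | 0.5 | 0.270 | 71.4% |
| 175 | 30% | 0.5 | 0.255 | 66.5% |

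For example, with c = 20% and b = 0.5 the difference is 0.30 × (1 − 0.20 × 0.5) = 0.27. With 250 per arm, z = 0.27/0.0894 = 3.02, which gives 85.5%.

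*Inflation from reporting.* Suppose there is no true one-month effect and the debriefing moves the arms' answers apart by 0.10 SD.

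- 250 per arm: z = 0.10/0.0894 = 1.12, rejection rate 20.1% instead of 5%.
- 175 per arm: z = 0.10/0.1069 = 0.94, rejection rate 15.5%.

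With 250 per arm, half that shift (0.05 SD, z = 0.56) gives 8.6%, and one and a half times that shift (0.15 SD, z = 1.68) gives 38.9%.

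These figures show what modest uptake or a modest reporting shift would do. They do not estimate either one in this trial.

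**The case against.** The strongest reply is that the harm depends on text that cannot be seen. The debriefing script is not given, and section 6.3 says participants are told the nature of the investigation in advance. Section 6.2 introduces both rationale texts with a single line and never says that each arm sees only its own. If controls read both, they already know that dropping safety behaviors is thought to help. Both arms also complete the safety-behavior questionnaire (SAFE) before and after treatment. This stands as a limit on how much new information the debriefing carries, and so on the size of the bias. It does not remove the exposure: a debriefing on the actual, full purpose would be expected to add something, such as which condition was the comparator.

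The second reply is that no stated analysis uses the one-month data. A 2 x 2 design has two time points, baseline and post-treatment are the natural pair, and the hypotheses in section 2.2 say nothing about durability. This is fair, and it makes the harm conditional on a one-month contrast being reported. A full repeat battery with its own incentive suggests that the data are meant to be used. Which time point is confirmatory can be left to the statistical analysis plan, and its absence here is not held against the protocol. The order of the components is fixed by the protocol itself.

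Third, early disclosure has ethical value, so the order is a trade-off and not a mistake of fact. That is accepted and weighs on the choice of remedy.

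**Conclusion.** The concern holds as a design weakness that should be fixed. As written, every one-month outcome is collected after both arms have been told the full purpose, so a one-month between-group difference cannot be read as a lasting effect of the intervention alone. The net direction of the bias is unknown and its size cannot be derived from the protocol. On the assumptions shown, uptake by 20–30% of controls takes power from 91.8% to between 89.0% and 65.1% with 250 per arm, and a 0.10 SD reporting shift raises false rejection to 15.5–20.1%. The conclusion rests on the listed order and on the debriefing revealing something new; it does not rest on these figures. The post-treatment comparison, and a 2 x 2 ANOVA using baseline and post-treatment, are not affected. Confidence is medium, because the debriefing content and any masking are not described.

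**What to change.** Move Component 7 to follow Component 8 in section 6.2. Debrief each participant once the one-month questionnaires are submitted, non-responders when the follow-up window closes, and those who withdraw at withdrawal. This needs a protocol amendment that reorders two components, made before participants are debriefed.

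The cost is that full disclosure comes later, by about one month if the follow-up label is taken literally. The exact interval is not settled: section 6.1 describes two weeks of checklists, while section 9.1 fits a four-week period and a one-month follow-up into six weeks in total. Sections 6.3 and 15.1 describe the risks as minimal, so the delay looks acceptable, subject to ethics review.

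If the early debriefing must stay, limit the randomised efficacy claim to post-treatment and report the one-month between-group contrast as descriptive and collected after debriefing. This costs nothing operationally and could be written into the statistical analysis plan if it is not already there. It labels the bias but does not remove it.

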7.0 Data and Specimen Banking*

- 7.1 *Data will be stored in de-identified databases in password protected files on encrypted computers.*
- 7.2 *Results from questionnaires and surveys will be stored.*
- 7.3 *Data will not be released.*

8.0 Sharing of Results with Subjects*

8.1 Individual results will not be shared with participants. Participants will be able to read resulting journal articles as they are published.

9.0 Study Timelines*

9.1 The total duration of an individual subject's participation in the study is 6 weeks. This will include an initial questionnaire battery, four week manipulation assessment period, and the post-treatment questionnaire's and one month follow up. We predict that it will take roughly 12-18 months to enroll all study subjects.

10.0 Subject Population*

10.1 Adults aged 18-65 recruited from across the United States

10.2 Inclusion Criteria: The primary inclusion criteria for this study will be elevated social anxiety symptoms as defined by a score of 30 or higher on the SPIN. The only software/hardware requirements are that participants have access to a smartphone or computer that is connected to the internet.

Exclusion Criteria: 1) Score of 29 or lower on the SPIN, 2) Currently receiving treatment (therapy, counseling, etc.) for anxiety or depression, 3) If applicable, unstable psychiatric medication usage any time over the past 4 weeks.

10.3 We will not include: Adults unable to consent, Individuals who are not yet adults (infants, children, teenagers), Pregnant women, or Prisoners.

